4. SUBJECT DISPOSITION

4.1. Subject Enrollment and Disposition

A summary of subject enrollment will be provided by initially randomized treatment group for each country, investigator within a country, and overall. The summary will present the number and percentage of subjects enrolled. For each column, the denominator for the percentage calculation will be the total number of subjects analyzed for that column.

A similar enrollment table will be provided by randomization stratum. The denominator for the percentage of subjects in the stratum will be the total number of enrolled subjects. If there are discrepancies in the value used for stratification assignment between the IXRS and the clinical database, the value collected in the clinical database or other source document will be used for the summary. A listing of subjects with discrepancies in the value used for stratification assignment between the IXRS and the clinical database or other source document at the time of data finalization will be provided.

The randomization schedule used for the study will be provided as an appendix to the CSR.

A summary of subject disposition will be provided by treatment group for both the entire study duration and by treatment phase. This summary will present the number of subjects in each of the categories listed below:

- Subjects screened
- Subjects randomized
- Safety Analysis Set
- Completed Study
- Prematurely discontinued study with reasons for discontinuation
- Completed study drug
- Prematurely discontinued study drug with reasons for discontinuation

The study and drug disposition will also be presented by study period with the following categories:

- Completed study up to Week 12, Week 24, and through the end of the study
- Completed study drug up to Week 12, Week 24, and through the end of study
- Did not complete the study/study drug up to Week 12, Week 24, and through the end of study with reasons for premature discontinuation of the study/study drug
- Re-randomized
- Continuing study drug (Week 12 analysis only)
- Continuing study (Week 12 analysis only)

For the status of study drug and study completion and reasons for premature discontinuation with the number and percentage of subjects in each category will be provided. The denominator for the percentage calculation will be the total number of subjects in the Safety Analysis Set corresponding to that column. In addition, a flowchart will be provided to depict the disposition.

For placebo subjects, completion of the study up to Week 12 will be based on the presence of the corresponding visit in EDC or presence of Early termination visit which is after Week 8 visit and the [date of ET visit – date of first dose + 1] \geq 82 days (target date for Week 12 visit – protocol allowed visit window). Subjects are considered to complete 12 weeks of treatment if the start date of Week 12 treatment is provided or the [last dose date – first dose date +1] \geq 82.

The by-subject listing of disposition will be provided by subject identification (ID) number in ascending order to support the above summary tables.

4.2. Extent of Study Drug Exposure and Adherence

Extent of exposure to study drug will be examined by assessing the total duration of exposure to study drug and the level of adherence to the study drug specified in the protocol.

4.2.1. Duration of Exposure to Study Drug

Total duration of exposure to study drug will be defined as last dosing date of any study drug minus first dosing date of any study drug plus 1, regardless of any temporary interruptions in study drug administration, and will be expressed in weeks using up to 1 decimal place (eg, 4.5 weeks). For Week 12 primary analysis, the data cut-off date can be used as the last dosing date for subjects continuing on study.

For subjects with a partial last dosing date (ie, month and year of last dose are known), the latest of the dispensing dates of study drug bottles, and the imputed last dose date [day imputed as last day of the month] will be used as the final imputed last dose date.

If only year is recorded (ie, month and day of last dose are missing) or the entire date is missing then the latest of the dispensing month of study drug bottles, study drug start month, and study drug bottle return month will be used to impute the unknown last dose month (and a year if the entire date is missing). With the month imputed, the aforementioned method will be used to impute the last dose date. If the imputed date is after the date of death, choose the death date.

In addition, the duration of active treatment will be provided. The calculation for the subjects originally randomized to placebo will include the period starting from the first day of active study drug (Week 12 treatment start date is recorded on CRF).

The total duration of exposure to study drug will be summarized using descriptive statistics (number of subjects [n], mean, SD, median, Q1, Q3, minimum, and maximum) and the percentage of subjects exposed through the following time periods: Day 1, Weeks 2, 4, 8, 12, 14, 16, 20, 24, 30, 36, 42, and 48. The subject is considered to be exposed up to Week X if the last dose of any study drug is at least visit target day (per [Table 3](#)) minus protocol-allowed window ([protocol Appendix 2](#)).

Summaries will be provided by treatment group for the Safety Analysis Set. No formal statistical testing is planned.

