- g) Estimated creatinine clearance (CL_{cr}) < 40 mL/min based on the Cockcroft-Gault formula

Subjects who discontinue study drug dosing at any time may continue with study visits, procedures, and assessments, if deemed medically appropriate by the investigator, but will not be eligible for entering the 24-week extension period. Subjects who permanently discontinue study drug for any reason will not be replaced.

Subjects withdrawing from the study should complete the early termination (ET) and FU visits. Subjects are free to withdraw from the study at any time without providing reason(s) for withdrawal and without prejudice to further treatment. The reason(s) for withdrawal will be documented in the electronic case report form (eCRF).

Reasonable efforts will be made to contact subjects who are lost to follow-up. All contacts and contact attempts must be documented in the subject's file.

The sponsor has the right to terminate the study at any time in case of safety concerns or if special circumstances concerning the study medication or the company itself occur, making further treatment of subjects impossible. In this event, the investigator(s) and relevant authorities will be informed of the reason for study termination.

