3.2. Subject Grouping

In the FAS and PP Analysis Set, subjects will be grouped according to the treatment to which they were initially randomized at Study Day 1. For the analyses based on the Safety Analysis Set, subjects will be grouped according to the actual treatment that they received. The actual treatment received will be considered to differ from the randomized treatment only when subject's actual treatment differs from randomized treatment for the entire treatment period.

For the analysis of the placebo-controlled period (up to week 12), subjects will be presented by three treatment groups:

- Filgotinib 200 mg
- Lanraplenib 30 mg
- Placebo

For the analyses for the entire study duration, subjects will be grouped into five treatment groups as specified in [Table 2](#).

Table 2. Treatment Groups for the Entire Study Duration

Lanraplenib 30 mg	Lanraplenib 30 mg from Study Day 1
Filgotinib 200 mg	Filgotinib 200 mg from Study Day 1
Placebo/Lanraplenib 30 mg	Placebo up to Week 12 and lanraplenib 30 mg after Week 12
Placebo/Filgotinib 200 mg	Placebo up to Week 12 and filgotinib 200 mg after Week 12
Placebo	Placebo group with study drug withdrawn prior to or at Week 12 (did not receive drug assigned at Week 12)

For the PK analyses, subjects will be grouped according to the actual treatment they received.

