The CTCAE will be used to assign toxicity grades (0 to 4) to laboratory results for analysis. Grade 0 includes all values that do not meet the criteria for an abnormality of at least Grade 1. For laboratory tests with criteria for both increased and decreased levels, analyses for each direction (ie, increased, decreased) will be presented separately.

7.2.2.1. **Treatment-Emergent Laboratory Abnormalities**

Treatment-emergent laboratory abnormalities for the entire study period and in subjects discontinued treatment prematurely are defined as values that increase at least 1 toxicity grade from baseline at any postbaseline time point, up to and including the date of last dose of study drug plus 30 days for subjects who permanently discontinued study drug, or the last available date in the database snapshot for subjects who were still on treatment at the time of an interim analysis. If the relevant baseline laboratory value is missing, any abnormality of at least Grade 1 observed within the time frame specified above will be considered treatment emergent.

For the analyses of active treatment period, the baseline is the day of the first dose of active study drug administration.

For the analyses of placebo-controlled period, the lab abnormality occurring after (within 30 days) Week 12 visit is included only if subject did not continue treatment after Week 12.

The listing of all laboratory abnormalities will be provided.

7.2.2.2. **Treatment-Emergent Marked Laboratory Abnormalities**

Treatment-emergent marked laboratory abnormalities are defined as values that increase from baseline by at least 3 toxicity grades at any postbaseline time point, up to and including the date of the last dose of study drug plus 30 days for subjects who permanently discontinued study drug or the last available date in the database snapshot for subjects who were still on treatment at the time of an primary Week 12 analysis. If the relevant baseline laboratory value is missing, any Grade 3 or 4 values observed within the timeframe specified above will be considered treatment-emergent marked abnormalities.

Same rules as in the Section 7.2.2.1 apply for determination of TE abnormality in the placebo-controlled and entire study duration.

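### At the Week 12 analysis, SAP 4.2.1 keys the cut-off rule for last dose to being on study rather than on drug, and total exposure has no end at the placebo switch (minor)

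*SAP*

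**What the plan says.** SAP 4.2.1 defines total exposure as "last dosing date of any study drug minus first dosing date of any study drug plus 1". For the Week 12 analysis it adds: "For Week 12 primary analysis, the data cut-off date can be used as the last dosing date for subjects continuing on study". It also gives imputation rules for partial and missing last dose dates, promises a separate duration of active treatment, and asks for summaries by treatment group without naming the grouping.

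Four other places bear on this:

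- Protocol 3.5.2: "Subjects who discontinue study drug dosing at any time may continue with study visits, procedures, and assessments", if the investigator finds this medically appropriate, but these subjects "will not be eligible for entering the 24-week extension period".
- SAP 4.1 lists two separate disposition categories for this same analysis: "Continuing study drug (Week 12 analysis only") and "Continuing study (Week 12 analysis only").
- SAP 7.2.2.2, the parallel rule for marked laboratory abnormalities, uses "the last available date in the database snapshot for subjects who were still on treatment at the time of an primary Week 12 analysis".
- SAP 3.2: "For the analysis of the placebo-controlled period (up to week 12), subjects will be presented by three treatment groups". For the entire study it uses five groups, with switched placebo subjects in their own columns.

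**The concern.** The rule is attached to the wrong status. A subject who stopped drug at Week 4 and still attends is on study, so the text allows the cut-off to become her last dose date. SAP 4.1 recognises the difference between the two statuses, and SAP 7.2.2.2 applies its equivalent rule only to those still on treatment. The word *can* adds discretion: two programmers could produce different exposure tables and both comply.

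A second gap lies in the exposure definition itself. The Week 12 analysis waits until every subject has reached Week 12 or left (SAP 2.2), so placebo subjects who enrolled early may have been on active drug for some time. Nothing ends total exposure at the switch. In a three-column table, the Placebo column could then exceed the 12 weeks of placebo the design provides.

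At stake is a correct reading of how long each arm was treated when the sponsor team reviews unblinded Week 12 safety results.

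**Working it through.** **Plan's own figures.** The documents give no exposure figure to reproduce. The stated 79% power is reproduced by a normal approximation with 18 versus 9 subjects after 10% drop-out: 2/(2 × √(1/9 + 1/18)) = 2.449; 2.449 − 1.645 = 0.804; power = 0.789. Exposure does not enter it.

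**Inputs from the documents.** Exposure in weeks = (last dose date − first dose date + 1)/7 (SAP 4.2.1). Active arms have 20 subjects (SAP 1.3). Target days are 85 for Week 12 and 169 for Week 24 (SAP 3.8.2), and the Week 12 visit window is ±3 days (protocol Appendix 2).

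**Assumptions.** Last dose on Day 29, and the cut-off positions shown, are illustrative. Day 169 is about the latest, because an off-drug subject's last scheduled visit is Week 24.

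**1. Off-drug subject still attending.** True exposure = 29/7 = 4.1 weeks. Rise in a 20-subject arm mean = k × (cut-off day − 29)/(7 × 20), where k is the number of such subjects.

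| Cut-off on her study day | Credited weeks | Excess weeks | Rise in mean, k = 1 | Rise in mean, k = 2 |
|---|---|---|---|---|
| 85 | 12.1 | 8.0 | 0.4 | 0.8 |
| 113 | 16.1 | 12.0 | 0.6 | 1.2 |
| 169 | 24.1 | 20.0 | 1.0 | 2.0 |

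**2. Percentage exposed through Week 12.** The threshold is 85 − 3 = Day 82, so any cut-off from Day 82 wrongly passes her. Take an arm whose other subjects all have 84 days, and credit her only to Day 84:

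- One such subject: the true mean is (29 + 19 × 84)/(20 × 7) = 11.6 weeks and is shown as 12.0; exposed through Week 12 goes from 95% to 100%.
- Two such subjects: the true mean is (2 × 29 + 18 × 84)/(20 × 7) = 11.2 weeks and is shown as 12.0; exposed through Week 12 goes from 90% to 100%.

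SAP 4.1 counts 12 weeks of treatment as complete if last dose minus first dose plus 1 is at least 82 days. If the derived date is reused there, she passes that test too.

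**3. Switched placebo subject.** Placebo exposure is 84/7 = 12.0 weeks. Total exposure to the cut-off can be anything from 12.1 to 48.0 weeks. The accrual period is not given. Assume even entry of nine switched subjects, a cut-off when the last of them reaches Week 12, and a cap at 48 weeks. Mean total exposure is then 12 + (accrual weeks)/2 until the cap applies:

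| Accrual (weeks) | Mean total (weeks) | Share on active drug |
|---|---|---|
| 0 | 12 | 0% |
| 12 | 18 | 33% |
| 24 | 24 | 50% |
| 36 | 30 | 60% |
| 52 (cap applies) | 35 | 66% |

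This reaches a Placebo column only under the three-group layout. Under the five-group layout none of it does.

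**The case against.** The best defence is that a sensible programmer would never do this. Protocol 8.6.1 takes exposure from the study drug administration page of the eCRF, so a subject who stopped should have a recorded last dose date. SAP 4.2.1's imputation rules presuppose such a date, and the cut-off rule is only permissive. This stands in part: over-crediting is allowed, not prescribed. But the SAP never says that the recorded date takes precedence.

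A reader might also infer more than the documents support:

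- *That off-drug subjects could be credited with 36 or 48 weeks.* They cannot enter the extension, so they are no longer on study then and the rule cannot apply.
- *That the cut-off rule puts active dosing in the Placebo column.* It does not. A true last dose date gives the same result, because the definition covers any study drug. The layout is also unstated. SAP 2.2 delivers the placebo-controlled-period analyses at Week 12, which points to three groups, but the SAP 4.2.1 time points run to Week 48, which fits five. Separate reporting of active-treatment duration mitigates the problem.
- *That Week 12 adverse event rates are biased.* The SAP 7.1.6 tables use numbers and percentages of subjects, and SAP 7.1.5.1 closes the Week 12 event window the day before Week 12 treatment starts. SAP 7 plans exposure adjustment only for adverse event analyses that include data after Week 12, and does not define the denominator.

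**Conclusion.** The point holds as a minor specification error. Read literally, SAP 4.2.1 lets off-drug time count as exposure, against the distinction drawn in SAP 4.1 and the narrower wording of SAP 7.2.2.2. For a last dose on Day 29, the distortion is at most about 20 weeks for the subject and 1.0 week per such subject in a 20-subject arm mean, plus a false count as exposed through Week 12. The number of such subjects and the cut-off timing are unknown.

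The missing end at the switch is a separate gap, and it matters only if the Week 12 exposure table has three columns. In that case the overstatement for placebo could be larger than the off-drug effect, depending on accrual time.

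The reach is limited to descriptive exposure summaries at the Week 12 analysis, and to the SAP 4.1 treatment-completion test if the derived date is reused.

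**What to change.** Amend SAP 4.2.1 along these lines:

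- *At the Week 12 analysis, the data cut-off date will be used as the last dosing date only for subjects continuing study drug at the cut-off. For all other subjects the recorded last dose date will be used or, if it is partial or missing, the date imputed under this section.*
- *In three-group summaries of the placebo-controlled period, exposure ends no later than the day before the Week 12 treatment start date.*

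Also state which treatment grouping the Week 12 exposure table uses.

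The cost is small. Drug status is already needed for SAP 4.1, and the Week 12 treatment start date is already on the CRF, so no new data are required. Programming needs a condition on drug status and, for three-group tables, a truncation date. Reported exposure will be lower, and substantially so for switched placebo subjects if a three-group table is used.

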3.6. Missing Data and Outliers

3.6.1. Missing Data

In general, missing data will not be imputed unless methods for handling missing data are specified. Exceptions are presented in this document.

For missing last dosing date of study drug, imputation rules are described in Section 4.2.1. The handling of missing or incomplete dates for AE onset is described in Section 7.1.5.2, and for prior and concomitant medications in Section 7.4. Imputation rules adopted in the efficacy analyses are specified in Section 6.

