7.1.5. Treatment-Emergent Adverse Events

7.1.5.1. Definition of Treatment-Emergent Adverse Events

Treatment-emergent adverse events (TEAEs) of the entire study duration are defined as 1 or both of the following:

- Any AEs with an onset date on or after any study drug start date and no later than 30 days after permanent discontinuation of any study drug
- Any AEs leading to premature discontinuation of study drug.

TEAEs up to Week12/24 are defined as 1 or both of the following:

- Any AEs with an onset date on or after Day 1, prior to start of Week 12/24 treatment and no later than the day before the Week 12/24 treatment start date. For subjects who discontinued treatment prior to Week 12/24 visit, any AEs with an onset date on or after the study drug start date and no later than 30 days after permanent discontinuation of study drug
- Any AEs leading to premature discontinuation of study drug prior to first Week 12/24 dosing

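### SAP 4.2.1 imputes a partial or missing last-dose date to month-end or later with death as the only ceiling, so it can record dosing after all drug was returned or the subject left the study

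*SAP*

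**What the plan says.** SAP 3.6.1 sends the reader to one place: "For missing last dosing date of study drug, imputation rules are described in Section 4.2.1". SAP 4.2.1 then has two branches.

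- **Month and year known.** The last dose is "the latest of the dispensing dates of study drug bottles, and the imputed last dose date [day imputed as last day of the month"]. The result is month-end, or later if a bottle was dispensed later.
- **Month missing, or whole date missing.** The latest of the dispensing month, "study drug start month, and study drug bottle return month will be used to impute the unknown last dose month". Month-end is then applied as in the first branch.

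The only ceiling is "If the imputed date is after the date of death, choose the death date". It closes the second branch, so its use in the first is implied, not stated.

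The last-dose date feeds several outputs:

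- total exposure and the percentage exposed through each week (SAP 4.2.1);
- the laboratory windows of last dose plus 30 days (SAP 7.2 and 7.2.2);
- the classification of concomitant medications (SAP 7.4.2);
- the completion rule in SAP 4.1: "Subjects are considered to complete 12 weeks of treatment if the start date of Week 12 treatment is provided", or if last dose date minus first dose date plus 1 is at least 82.

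Protocol 5.8 requires all dispensed drug, used and unused, to be returned and the return date logged. SAP 4.1 itself uses the ET visit date, for completion of the study by placebo subjects.

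**The concern.** A subject cannot take study drug after handing all of it back, and the study cannot record dosing after the subject has left. Those dates bound the last dose from above, yet neither branch uses them as a bound. In the second branch the return month can only move the imputed month later, never earlier.

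The direction of the error is fixed: apart from the death ceiling, the imputed date is the latest the recorded month allows, or later. For a subject who stopped early, this lengthens apparent exposure and may carry the subject across a week threshold. One subject is 1/20 = 5 percentage points of a planned active arm and 1/10 = 10 points of the planned placebo arm.

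**Working it through.** **The plan's own threshold.** SAP 4.1 builds the 82 days from "target date for Week 12 visit – protocol allowed visit window". The Week 12 target is Day 85 (SAP Table 3) and the window is ± 3 days (Protocol Appendix 2): 85 − 3 = 82. Reproduced.

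**Size of the overstatement, month known.** Assume no later dispensing date and a true last-dose day uniform over a 365-day year. In a month of L days the excess runs from 0 to L − 1 and totals L(L − 1)/2.

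- Seven 31-day months: 7 × 31 × 30/2 = 3,255
- Four 30-day months: 4 × 30 × 29/2 = 1,740
- One 28-day month: 28 × 27/2 = 378

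The mean excess is (3,255 + 1,740 + 378)/365 = 5,373/365 = 14.7 days. The maximum is 30.

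**Month missing.** If the return month is the latest candidate, the imputed date is the end of that month. It falls after the return date unless drug came back on the last day of a month: (365 − 12)/365 = 97% of return dates. The excess over the true last dose can exceed 30 days here if drug was returned in a later month than the last dose.

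**Dosing after return, an example.** First dose 8 January 2018; true last dose 2 March (Day 54); drug returned 5 March (Day 57, an assumed 3-day lag); only March 2018 recorded. The imputed last dose is 31 March, Day 83. That is 26 days after return. Exposure becomes 83/7 = 11.9 weeks instead of 54/7 = 7.7, and 83 ≥ 82 meets the completion rule if the imputed date is used there.

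**A second example.** With first dose 10 April as Day 1, 1 June is Day 53 and 30 June is Day 82. Any true last dose from 1 to 29 June (Days 53 to 81) recorded only as June becomes Day 82.

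**How early a stop can cross Day 82.** The excess is at most 30 days, so the earliest is Day 82 − 30 = Day 52, and only when Day 52 is the first of a 31-day month (7/365 = 2%). Taking all 365 first-dose dates in 2018:

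| True last-dose day | Share of first-dose dates imputed to Day 82 or later |
|---|---|
| 51 | 0% |
| 52 | 2% |
| 60 | 28% |
| 70 | 61% |
| 80 | 93% |

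The average is 49% over Days 52 to 81. Spread over Days 29 to 81 it is 0.4907 × 30/53 = 28%. Both are conditional on a partial date already existing and on evenly spread stop days.

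**Effect of a return-date cap, Days 52 to 81, by assumed return lag.**

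| Lag from last dose to return | Still imputed to Day 82 or later |
|---|---|
| no cap | 49% |
| 0 days | 0% |
| 3 days | 9% |
| 7 days | 20% |
| 14 days | 35% |

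The cap always prevents dosing after final return. It does not by itself cure the completion count.

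**The case against.** The strongest reply is that this is a fallback rule that may seldom or never be used. Source records must hold the start and end dates of study drug (Protocol 9.1.5), entries are source-verified and queried (9.1.6), and queries are resolved or adjudicated before the final analysis (SAP 2.3). Subjects who attend a return or ET visit are the least likely to have a partial date. Those who do have one may be lost to follow-up or may not have returned their bottles, a case SAP 4.2.2 foresees; a cap then has nothing to work with. A subject who stops drug but stays in the study (Protocol 3.5.2) is not limited by an exit date either. All of this stands. It limits the size of the problem but does not make the written rule right when a return or exit date does exist.

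A reader might infer more than the documents support in four ways.

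- *That early stoppers will be counted as 12-week completers, at a rate near 28%.* SAP 4.1 does not say that imputed dates enter the completion rule; this is inferred from SAP 3.6.1 and the absence of another rule. The sentence before it is limited to placebo subjects, so its scope is unclear. The 28% is conditional on an assumed stop distribution and is not an expected error rate. Disposition tables also report premature drug discontinuation with reasons, so a contradiction would be visible.
- *That the TEAE window is stretched.* The main definition in SAP 7.1.5.1 runs to "no later than 30 days after permanent discontinuation of any study drug" and does not name the imputed date. AE collection ends 30 days after the last administration (Protocol 7.3.1), so for a subject who left there is little extra to capture.
- *That exposure-adjusted event rates move materially.* Fifteen days against a planned 20 × 336 = 6,720 subject-days is about 0.2% per affected subject.
- *That only early stoppers are affected.* The rule covers any partial last-dose date, including those of subjects who finish Week 24 or Week 48, whose 12-week status cannot change.

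**Conclusion.** The point holds as a minor defect. As written, SAP 4.2.1 can place the last dose after all study drug was returned or after the subject left the study. With the month known and no later dispensing date, the excess is 0 to 30 days, about 15 on average if the true day is uniform. It can inflate exposure duration, the percentages exposed through each week and the laboratory window. It can inflate the 12-week treatment completion count only if imputed dates are used in SAP 4.1.

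The number of subjects affected is not given and is probably small. The outputs concerned are descriptive. The primary treatment-policy analysis uses all observed values whatever happens to treatment, with nominal visits, so it does not change. The supportive hypothetical-estimand analysis could be touched only if the imputed date were used to time discontinuation, which the SAP does not say.

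**What to change.** Add to SAP 4.2.1, for both the month-known and the month-missing branches:

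> *The imputed last dose date will not be later than the earliest available of the date all study drug was returned, the date of study discontinuation or ET visit, and the date of death.*

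Add to SAP 4.1 that, where the last-dose date is partial or missing, completion of 12 weeks of treatment is taken from the CRF study drug disposition record and not from the imputed date. This is needed because the cap alone leaves some misclassification when return lags the last dose.

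The cost is two sentences, using dates and disposition data already collected. Reported exposure and follow-up windows become slightly shorter for the affected subjects. Where no return or exit date was recorded, the cap has no effect.
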